Brief Cognitive Behavioral Therapy for Chronic Pain to Improve Functional Outcomes among Primary Care Veterans

NCT04724694

10/17/2024

Background and Significance

Chronic pain is highly prevalent among primary care Veterans and impacts health and safety.

Pain has a significant impact on the VA healthcare system with 50% or more of Veterans in primary care reporting pain (1-2). Chronic musculoskeletal conditions are among the most common sources of pain and are, therefore, the focus of this application. Chronic musculoskeletal pain has been associated with a range of disabling health outcomes, including diminished functional status and quality of life as well as increased health care costs associated with high rates of medical care utilization (3-5). Attention to chronic pain among Veterans has also increased given its relation to high priority safety issues identified by VA: suicide and opioid use. Chronic pain is associated with suicide risk, particularly among those with moderate or severe pain intensity (6). The safety of opioids has also been called into question because of well-documented adverse outcomes including substance misuse, accidental poisoning, and death (7).

Cognitive Behavioral Therapy for Chronic Pain (CBT-CP) is effective but designed for specialty care.

The CBT-CP treatment approach is consistent with the biopsychosocial model of pain and targets the biological (e.g., relaxation training), psychological (e.g., cognitive coping), and social (e.g., decreasing isolation) aspects of pain to improve health outcomes. CBT-CP encourages clients to adopt an active, problem-solving approach to cope with the many challenges associated with chronic pain (8). Behavioral targets of CBT-CP emphasize activity pacing that helps with re-engaging in pleasurable events (or new activities) in a safer manner. Relaxation training is used to directly address the stress associated with chronic pain. CBT-CP also targets the maladaptive thoughts that occur in relation to pain. Learning and applying thought monitoring, evaluation, and disputation can result in more balanced and useful ways of responding to pain and its consequences. Abundant evidence suggests that CBT-CP produces small to moderate improvements in important clinical outcomes, including measures of disability (e.g., pain-related activity interference), pain intensity, mood (e.g., depression symptoms), and quality of life (9).

Within the VA system, a protocolized full-length CBT-CP treatment is currently available as part of the Evidence-Based Psychotherapy Program which has been shown to be effective at improving pain intensity, catastrophic thinking, pain-related activity interference, and overall psychological distress. This protocol is typically delivered by behavioral health providers with pain management expertise who work in specialty care settings due to its time-intensive nature (i.e., 11-12 sessions of 50-minutes each). Many patients who could benefit from CBT-CP never receive it due to limited access to specialty

CBT-CP providers (10). Adding more specialty providers is likely beneficial to a point, but the sheer volume of patients who could benefit from CBT-CP prohibit specialty care from being the chief source of CBT-CP. Thus, there has been a suggestion for improved integration of behavioral treatment into medical settings, such as primary care, to reach more patients in need.

Brief CBT-CP provides essential components of treatment in less time.

Our team adapted the full-length protocol into *Brief Cognitive Behavioral Therapy for Chronic Pain (Brief CBT-CP)* (11) which is designed for use by Primary Care Mental Health Integration (PCMHI) providers to

reduce functional limitations related to pain while conforming to the brief treatment format (≤ 6 , 15-30-minute appointments). Brief CBT-CP is significantly shorter in duration (~3 hours total) than the original protocol (up to 12 hours). The resulting manualized protocol for Brief CBT-CP is summarized in Figure 1.

Preliminary studies: Brief CBT-CP is associated with improvement in patient outcomes.

Figure 1: Overview of Brief CBT-CP Sessions

Session	Content summary
1	Education and Goal Identification: Acute versus chronic pain; factors that impact pain/biopsychosocial model; chronic pain cycle; SMART goals
2	Activities and Pacing: Address fear of movement; activities pacing; avoiding withdrawal or disengagement
3	Relaxation Training: Relaxation benefits and techniques (Deep breathing and abbreviated progressive muscle relaxation)
4	Cognitive Coping 1: Recognize unhelpful thoughts that negatively impact the pain experience
5	Cognitive Coping 2: Modify thoughts that are unhelpful when managing pain
6	The Pain Action Plan: Reviewing progress made and skills acquired; Plan for future success

We conducted a clinical demonstration project to gather preliminary data regarding Brief CBT-CP effectiveness and acceptability among patients and providers (12). Nationally, 22 PCMH providers across 22 primary care clinics responded to an invitation to participate in a 12-month demonstration project that included training in Brief CBT-CP. At the end of the project period, data from 118 unique patients treated with Brief CBT-CP by a participating PCMH provider were analyzed to assess changes in outcomes. Although not a randomized controlled trial (RCT), patient reported outcome data collected by the PCMH providers at each visit showed statistically significant improvement in the PEG (13) of moderate effect size by session three ($d = 0.65$). This one-point decrease in PEG scores indicated that clinically significant improvement in outcomes can potentially be made in as few as three, 30-minute appointments of Brief CBT-CP. Pain self-efficacy showed smaller but also statistically significant improvements ($d = 0.22$).

Significance and Relevance for Veterans and VA Healthcare

The long-term goal of this research is to promote recovery among Veterans with chronic musculoskeletal pain. The focus of the intervention (i.e., a CBT intervention to improve functional outcomes commonly impacted by chronic pain) directly addresses the current RR&D special emphasis area related to non-pharmacological activity-based interventions for chronic pain. Taken together, these related high priority topics reflect ORD-wide clinical priorities and the VA's current Strategic Plan (FY19-24).

Research Design and Methods

Participants.

We will recruit and randomize 184 Veterans (not including screening failures) who utilize one of the primary care clinics located at the regional VAMC and CBOCs in Western and Central New York. Eligible participants will be randomized in a 1:1 ratio into either (1) Brief CBT-CP plus primary care TAU or (2) primary care TAU only.

Eligibility and recruitment.

Screening procedures. Our primary method of recruiting Veterans with chronic musculoskeletal pain who self-report functional impairment will replicate our successful case-finding method. This method has proven especially effective in identifying primary care patients with chronic pain of at least moderate intensity that could benefit from intervention but who have not otherwise received behavioral treatment for pain. Note that we will additionally accept referrals for potential participants directly from the primary care team, should they arise or directly from the Veteran by contacting the PI or study staff after hearing of the study by word of mouth or other sources, including ClinicalTrials.gov. For case-finding, VA electronic medical record data will be initiated to identify potential participants. Based on prior work, we estimate that about 7,000 individuals will initially be accessed through VINCI/CPRS from which to do additional screening for *initial eligibility criteria*: Veterans who are age ≥ 18 and ≤ 79 years, conversant in English, have an established history of VA primary care utilization at the regional VAMC/CBOCs (i.e., at least one primary care visit in the past year), and a diagnosis of a musculoskeletal condition based on ICD-10 code linked to their primary care encounter(s). We will also remove patients with a diagnosed major or minor neurocognitive disorder (e.g., dementia) based on ICD-10 code. Those Veterans meeting initial eligibility criteria will be sent a study invitation letter signed by the primary care lead. Following the letter, Veterans will be contacted by phone (after a period of one week to allow patients to decline participation, if desired) for additional screening. They are first asked to verify the presence of current musculoskeletal pain for ≥ 3 months (consistent with the consensus definition of chronic pain from the International Association for the Study of Pain). The PEG (13), a well-validated 3-item composite measure of pain intensity and functional impairment, will also be administered. Veterans must score ≥ 4 on the PEG pain intensity item and ≥ 4 on the PEG pain interference items to verify impact of at least moderate intensity. *Initial exclusion criteria*: Veterans will be excluded if they score positive on the Drug Abuse Screening Test (DAST-10). We will exclude those with a positive score on the Alcohol Use Disorders Identification Test (AUDIT) which would exclude those with a more significant alcohol use disorder. Veterans will be additionally excluded at this stage if they self-report current or prior engagement (in the past 12 months) in behavioral health services specifically for chronic pain, such as pain psychology services or behavioral medicine interventions, given the potential for overlap in content with Brief CBT-CP. Veterans who are already receiving a stable course of on-going mental health services that are not focused on pain (e.g., PCMH, specialty mental health clinic, PTSD clinic, etc.) or psychopharmacological intervention from a mental health prescriber will not be excluded. We will ask patients to clarify if they have had any recent changes (last 2 months) in pain medication or medications for mental health conditions. Use of over-the-counter (OTC) analgesic medications/topicals will not be considered an exclusion criterion, even if these agents are recorded in the

patient's medical record by a VA provider. Similarly, routine or PRN use of prescribed anti-inflammatory medications (i.e., acetaminophen, aspirin, ibuprofen, naproxen, diclofenac) or topical agents will not be considered an exclusion criterion. Veterans who are engaging in interventional procedures for chronic pain management (e.g., epidural), have recently had (i.e., in the past three months) or plan to have surgery or other hospitalizations, or have a pending pain-related disability claim will be excluded.

Consenting and baseline assessment. We will aim to conduct all study procedures by phone/VVC as the safest option during the pandemic. We have therefore requested a waiver of documentation of informed consent and a full HIPAA waiver. Veterans who meet initial telephone screening criteria will be scheduled for consenting procedures and a baseline interview to confirm eligibility. We will send potential participants study related materials (e.g., baseline appointment reminder letter, informed consent information, etc.) in advance of their baseline appointment using secure Azure RMS email, a VA-approved encrypted email, or through standard mail. We will also send study measures in advance of the baseline and subsequent assessments based on request of the participant or judgment of the study team. Verbal consent will be and a check of participant understanding of key consent items will be administered prior to collecting baseline assessment data. Our primary outcome, pain-related activity interference, will be assessed with the Brief Pain Inventory (BPI) interference subscale. Only those potential participants with a score ≥ 4 (indicating at least moderate pain-related disability) will be included. Potential participants who endorse active suicidal ideation at time of assessment will be further evaluated by study staff following a standard suicide risk prevention protocol and consultation with study PI (or designee). Individuals who are deemed at elevated risk (e.g., suicidal ideation with intent and plan) will be connected to the appropriate emergency service (see Suicide Protocol, including warm handoff procedures to Vet's Crisis Line). Electronic medical record review will be used to confirm screening self-report of prescribed pain or psychiatric medications are on a stable dose for the past two months. Use of over-the-counter (OTC) analgesic medications/topicals will not be considered an exclusion criterion, even if these agents are recorded in the patient's medical record by a VA provider. Similarly, routine or PRN use of prescribed anti-inflammatory medications (i.e., acetaminophen, aspirin, ibuprofen, naproxen, diclofenac) or topical agents will not be considered an exclusion criterion. Patients will be asked to confirm medical record information regarding psychotropic medication, such as whether or not medications are currently being taken as prescribed. Similarly, chart review will be used to confirm select telephone screening items noted above, i.e., that the patient has not 1) used behavioral services for chronic pain management in the past 12 months, 2) has no recent (i.e., in the past three months) or upcoming interventional procedures for chronic pain management (e.g., epidural), 3) have recently had (i.e., in the past three months) or plan to have surgery or other hospitalizations, or 4) have a pending pain-related disability claim. Additionally, patients will be excluded if chart review indicates either of the following: 1) unstable psychiatric status (e.g., active psychosis, current mania), 2) major or minor neurocognitive disorder (e.g., dementia), or any other illness or condition (e.g., active cancer treatment for new diagnosis, end-of-life care, etc.) that would preclude or predictably influence ability to appropriately engage in study visits, as determined by the study team. Participants will also be excluded if they are unwilling to have their treatment sessions audio recorded. Patients who are excluded at this stage due to recent changes in medications, use of mental health services for chronic pain management within the past year, or recent/upcoming interventional procedures who otherwise meet all inclusion criteria and are interested in participating will be asked if they would like to be re-contacted in the future by study staff when appropriate timeframes have passed for re-evaluation of eligibility.

Procedures.

Upon completing baseline measures and meeting all eligibility criteria, participants will be randomly assigned to (1) Brief CBT-CP plus TAU or (2) TAU only. Assignment to Brief CBT-CP will be stratified based on degree of pain interference as measured by the Brief Pain Inventory (14). Participants will be classified as moderate interference (mean BPI interference subscale score ≥ 4 and < 7) or severe interference (mean BPI interference subscale score ≥ 7). All participants will complete a follow-up (face-to-face, telephone, or VVC) with the study coordinator, who will be blinded to participants' condition at 12 weeks (post-treatment) randomization for re-administration of study measures. On an as-needed basis, we will contact participants through telephone, secure Azure RMS email, or through standard mail to provide appointment reminders and follow-up in case of missed appointments. Participants will be compensated \$50 for the initial assessment and \$50 for each of three follow ups (total \$200).

Measures of Patient Outcomes.

Administration of all study measures below will take about one hour at each time point:

Brief Pain Inventory (BPI). The BPI is an extensively validated 9-item scale that includes a subscale to assess pain-related interference in daily activities and social functioning (14). It is the primary patient outcome for this trial. The BPI also includes an assessment of pain intensity which will be used as a secondary outcome. Both subscales are considered core outcome measures for pain management effectiveness trials.

Patient Health Questionnaire-9 (PHQ-9). This is a 9-item measure of depressive symptoms validated for use in primary care (15). Respondents are asked to rate symptoms experienced over the past two weeks on a four-point scale ranging from not at all (0) to nearly every day (3). The PHQ-9 is included because depression, as an indicator of emotional functioning, is a core outcome domain for all pain clinical trials.

World Health Organization Quality of Life - BREF (WHOQOL-BREF). This 26-item abbreviated version of the well-validated, full-length WHOQOL measure evaluates quality of life in several domains such as social relationships and satisfaction with person-environment interactions (16). WHOQOL-BREF is included to determine if Brief CBT-CP can improve overall quality of life across multiple domains of function.

Ability to Participate in Social Roles and Activities – Short Form (APSRA-SF). This 8-item measure was developed to evaluate one's perceived ability to perform usual social roles and activities. Negatively worded items about social role engagement are rated on a scale from 1 (always) to 5 (never) such that higher scores represent fewer limitations. This measure has been shown to have excellent psychometric properties and clinical utility (17).

Demographics. We will gather participant background information by asking them to self-report standard demographic variables (e.g., age, gender, race/ethnicity, income, education, service era, etc.) for purposes of describing our sample and for potential effect modifiers (i.e., age and gender).

Therapist training and assessment of fidelity.

The interventionists will be trained by the PI in how to apply the protocol. Training will include at least 20 hours of didactic explanations of the principles of each intervention, role play and feedback exercises, discussion of case examples, and skill rehearsal. Following the above training requirements, audio recorded sessions will be reviewed from the first three patients assigned to each interventionist during weekly supervision to provide additional feedback/instruction based on rating scale scores. As shown in the Brief CBT-CP Adherence Ratings Scale, critical components are protocol-specific aspects of the intervention related directly to psychoeducation or skill development (e.g., describing the biopsychosocial model of pain or providing instruction in relaxation training). Non-critical components (e.g., agenda setting, reinforcing at-home practice, session length) are important aspects of most CBT-based treatment for the PCMH setting but are not intervention specific and, therefore, do not necessarily adversely impact dose of CBT. If adherence measure scores are below cut off, the interventionist will receive feedback and be assigned additional role play/training cases until deficiencies are corrected.

Study conditions.

Brief CBT-CP plus TAU: In summary, Brief CBT-CP is a manualized protocol that includes six, 30-minute sessions over the course of 12 weeks. Session one focuses on foundational pain education and the development of treatment goals. Session two emphasizes balanced engagement in physical activity and pleasurable events. Session three emphasizes skills training for easily implemented relaxation techniques. Sessions four and five focus on recognizing and modifying unhelpful thoughts that negatively impact pain. Session six focuses on relapse prevention and independent implementation of CBT-CP skills following treatment. Progress across sessions is measured by routine use of the PEG and two items inquiring about completing homework and skills practice. These brief items are administered by the study interventionists as part of the treatment protocol. Brief CBT-CP will be delivered face-to-face (primary care clinics or reserved clinical research space), telephone, or VVC depending on patient preference and safety issues related to COVID-19. Patients will be provided with the Brief CBT-CP Patient Guidebook as part of their treatment. Sessions will be audio recorded for review by PI or designee for fidelity assessment.

TAU only: Participants assigned to TAU only will receive standard medical care from their primary care provider including pain medications, brief advice (e.g., use of relative rest and self-care strategies), or referral to adjunctive interventions (e.g., physical therapy, chiropractic, standard PCMH, etc.), as indicated.

Power Analyses.

Our primary aim of this longitudinal, two-arm, parallel RCT is to adequately test our primary null hypothesis of no differences in pain-related activity interference measured by the BPI Interference (BPI-I) subscale between Brief CBT-CP plus TAU and TAU-only across a 12-week treatment period. Multilevel

modeling (MLM) using a random coefficients model will be used to test this hypothesis by assessing the group by time fixed effect coefficient. A sample size of 184 (92 per group) offers at least 80% power to detect a small to medium effect of .35 in the group by time coefficient with an experiment-wise alpha of .05 (2-tailed). To estimate sample size, we employed the method proposed by Hedeker, et al. for multilevel longitudinal designs (18) using results from our Brief CBT-CP clinical demonstration project. Our sample size is adjusted for an overall 25% attrition rate split across treatment (12%) and follow-up (13%) study periods.

Statistical Analysis

Statistical analyses will be conducted using SAS v9.4. The primary analysis will be conducted using the intention-to-treat approach; participants who are randomized will be analyzed according to their assigned group regardless of amount of treatment received. The data will be screened for missing cases, outlier scores, and non-normal response distributions. Assumptions underlying statistical models will be assessed by examining standardized residuals, influence diagnostics, and homogeneity of variance (e.g., among groups).

A multilevel model (MLM) will be used to test the primary null hypothesis of no difference in pain-related activity interference measured by the BPI Interference subscale between Brief CBT-CP plus TAU and TAU-only against the two-sided alternative. Our MLM will consist of fixed and random effects. Fixed effects will consist of group, time of assessment, and a cross-level interaction between condition and time. The condition effect compares the baseline BPI-I score between Brief CBT-CP plus TAU and TAU-only. Time will be entered in our model as a nominal variable representing effects relative to baseline at weeks. In other words, baseline (t0) will be defined as the reference level allowing dummy indicators to estimate differences in BPI-I from baseline. The β of the 12-week primary treatment effect will be tested against a two-sided alternative.

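### Assignment is stratified on baseline BPI interference, but the primary 12-week contrast adjusts for neither the stratum nor baseline severity, so precision is lost and, if strata are blocked, the standard error is somewhat too wide

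*Combined protocol and SAP*

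**What the plan says.** All references are to the combined protocol and SAP.

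- **Participants:** "Eligible participants will be randomized in a 1:1 ratio".
- **Procedures:** "Assignment to Brief CBT-CP will be stratified based on degree of pain interference as measured by the Brief Pain Inventory (14". The two strata are mean BPI interference from 4 to below 7, and 7 or more. The section does not say how assignment is balanced within a stratum (permuted blocks or otherwise).
- **Statistical Analysis, primary model:** "Fixed effects will consist of group, time of assessment, and a cross-level interaction between condition and time". Neither the stratum nor a baseline covariate is named.
- **Same section, baseline:** "The condition effect compares the baseline BPI-I score between Brief CBT-CP plus TAU and TAU-only", so the arms' baseline means are estimated freely. Time is nominal, and "baseline (t0) will be defined as the reference level allowing dummy indicators to estimate differences in BPI-I from baseline". The primary test is on the 12-week coefficient.
- **Power Analyses:** "A sample size of 184 (92 per group) offers at least 80% power to detect a small to medium effect of .35", "with an experiment-wise alpha of .05 (2-tailed", with the sample "adjusted for an overall 25% attrition rate split across treatment (12%) and follow-up (13%) study periods".

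**The concern.** Stratifying on baseline BPI-I treats it as prognostic, but the planned contrast does not use that information. When the baseline group difference is free and time is nominal, the group-by-week-12 coefficient is change in one arm minus change in the other. People with higher baseline scores usually change by a different amount, and that predictable variation stays in the error term.

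A second effect depends on the unstated allocation method. If allocation is balanced within strata, the design has already removed most chance imbalance between strata. The model does not know this and still counts it, so its standard error is too wide. If allocation is not balanced within strata, the standard error is right but the precision is still lost.

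At stake are a wider interval and some power on the primary outcome. The validity of the test is not in question.

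**Working it through.** **1. The plan's own figure.** A plain two-mean comparison at 0.35 needs 2(1.960 + 0.842)²/0.35² = 128.1, so 129 per arm: 258 in all, or 258/0.75 = 344 after 25% attrition. The planned 184 must therefore rely on correlation between occasions. If 0.35 is in raw-SD units and the SDs are equal, the change contrast needs 128.1 × 2(1 − ρ) per arm. Setting this to 92, 81 (12% loss) or 69 (25% loss) gives ρ of about 0.64, 0.68 or 0.73. So 184 is attainable but cannot be confirmed, because the plan states no correlation or variance. The point here does not depend on it.

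**2. Inputs.** From the documents: 184 randomised 1:1, entry at BPI-I of 4 or more, strata cut at 7, 12% loss during treatment (92 × 0.88 ≈ 81 per arm), two-sided 0.05. Assumed: baseline normal (mean 5.5, SD 2.2) cut to 4–10, which gives variance 2.10, 31% in the severe stratum, and a stratum that explains 68% of baseline variance; slope b of week-12 on baseline BPI-I of 0.5, 0.7 or 0.8; residual SD of 1.2, 1.5 or 1.8.

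**3. Formulas,** with n per arm:
- Reported variance of the planned contrast: (2/n)[(1 − b)² Var(Y0) + σ²].
- True variance if strata are balanced, which is also roughly what stratum by time reports: (2/n)[(1 − b)²(1 − 0.68) Var(Y0) + σ²].
- With continuous baseline: (2/n)σ².

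**4. One case in full (b = 0.5, σ = 1.5).** Here (1 − b)² Var(Y0) = 0.25 × 2.10 = 0.526.
- As written: √[(2/81)(0.526 + 2.25)] = 0.262.
- Balanced strata: √[(2/81)(0.526 × 0.32 + 2.25)] = 0.244.
- Continuous baseline: 1.5 × √(2/81) = 0.236.

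Simulation (6,000 trials, 12% missing, blocks of 4) gave reported SEs of 0.2617, 0.2443 and 0.2359. The true SE of the planned contrast was 0.2475, a little above 0.244 because small blocks and missing scores leave the balance imperfect.

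**5. All cases.** The cuts are from the formulas in step 3.

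| b | σ | correlation | reported/true SE, blocked (simulated) | same, exact balance (formula) | SE cut, stratum by time | SE cut, continuous baseline |
|---|---|---|---|---|---|---|
| 0.5 | 1.2 | 0.52 | 1.085 | 1.106 | 9.5% | 14.4% |
| 0.5 | 1.5 | 0.44 | 1.057 | 1.071 | 6.7% | 10.0% |
| 0.5 | 1.8 | 0.37 | 1.041 | 1.051 | 4.9% | 7.2% |
| 0.7 | 1.2 | 0.65 | 1.033 | 1.042 | 4.0% | 6.0% |
| 0.7 | 1.5 | 0.56 | 1.021 | 1.027 | 2.7% | 4.0% |
| 0.7 | 1.8 | 0.49 | 1.014 | 1.019 | 1.9% | 2.8% |
| 0.8 | 1.2 | 0.70 | 1.015 | 1.019 | 1.9% | 2.8% |
| 0.8 | 1.5 | 0.61 | 1.009 | 1.012 | 1.2% | 1.8% |
| 0.8 | 1.8 | 0.54 | 1.006 | 1.009 | 0.9% | 1.3% |

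Simulated cuts, over both allocation methods, were 0.6% to 9.6% for stratum by time and 0.9% to 14.3% for continuous baseline. Type I error of the planned test was 3.3% to 4.9% with blocks. Without within-stratum balance the SE ratio was 0.99 to 1.00 and type I error 4.8% to 5.3%, so the excess width comes from the balance.

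**6. Power** for an assumed 0.7-point effect (σ = 1.5, blocked, simulated):

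| b | as written | stratum by time | continuous baseline |
|---|---|---|---|
| 0.5 | 77.5% | 81.4% | 84.3% |
| 0.7 | 81.0% | 82.2% | 83.5% |
| 0.8 | 83.1% | 83.5% | 83.7% |

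**7. A second simulation** fitted group by time with unstructured covariance by maximum likelihood (10,000 runs, 12% missing). With b = 0.5, σ = 1.8 and blocks of 4, the reported SE was 0.303 against a true 0.289, and type I error was 4.1%. Power for 0.8 points was 75.7% as planned, 78.2% with change adjusted for stratum, and 79.8% with baseline as covariate.

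**8. Which term helps.** In a two-occasion random-intercept fit (b = 0.5, σ = 1.5, complete data), the group-by-time SE was 0.2470 without the stratum, 0.2470 with a stratum main effect, and 0.2302 with stratum by time. A main effect cancels out of a within-person contrast.

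**The case against.** The strongest reply is that this is a choice between two legitimate estimators. The planned test is valid or slightly conservative. The trial is powered on the contrast it will analyse, so the stated 80% may already pay for not adjusting, and the 0.7-point effect is not tied to the plan's 0.35. All of that stands: no shortfall against the plan is shown.

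The larger figures also sit at low correlations. If 184 needs a correlation of 0.64 to 0.73, only two scenarios qualify (0.65 and 0.70), with gains of about 6% and 3%. This fairly warns against leading with 14%. But those required correlations assume equal SDs, and under that same reading the cut is 1 − √[(1 + ρ)/2]: 9.4% at 0.64 and 7.0% at 0.73. The entry cut-off at 4 makes the equal-SD figures somewhat too high.

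Two technical limits also stand. With 6,000 trials the Monte Carlo error of an empirical SE is about 1/√12,000 = 0.9%, so simulated ratios up to 1.015 are not separable from 1; there the sign and size rest on the formula. And the plan names a random coefficients model and pays for three follow-ups, whereas the checks used two occasions. With complete data and a free mean for each arm and visit, the estimate is still the difference in mean change, but its model SE will depend on the covariance structure chosen.

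Finally, with missing week-12 scores the planned model does use baseline to predict them. At 12% missing this left the SE excess almost unchanged.

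**Conclusion.** The concern holds. As written, the primary contrast ignores a prognostic variable that the design itself stratifies on. The loss of precision arises under either allocation method; the over-wide standard error arises only if allocation is balanced within strata, which the plan does not state. The loss can be negligible or can reach about 14% of the standard error, and it vanishes as the slope of week-12 on baseline BPI-I approaches 1. In power it ranged from under 1 point to about 7 points in the cases shown. All of this rests on assumed SDs, slopes and baseline distribution. No bias or inflated type I error is claimed, and no SE excess for the secondary outcomes. The change is worth making because it is cheap and concerns the primary endpoint, not because the planned test is wrong.

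**What to change.** 1. In Procedures, state how allocation is balanced within the two strata.
2. In Statistical Analysis, prespecify one of these for the primary model:
   - **Preferred:** post-baseline BPI-I as response and continuous baseline BPI-I as covariate, with baseline by time if more than one follow-up is analysed. Adding the stratum then gains nothing (reported SE 0.2365 with it, 0.2359 without, at b = 0.5, σ = 1.5).
   - **If baseline stays a response:** include the stratum and stratum by time. With blocked strata this mainly corrects the reported SE; continuous baseline also lowers the true one.
   - **Equally acceptable, not simulated here:** keep baseline as a response and constrain the arms' baseline means to be equal.
3. The stratum in the secondary models is optional, for consistency with the design.

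The cost is a sentence or two of text, one or two model terms and no new data. The preferred model drops participants with no post-baseline score from the likelihood, which should be squared with the intention-to-treat statement; the other two options keep them. The choice should be fixed before outcomes are examined by arm. If baseline adjustment of the primary model is already requested in another comment, treat the two as one.
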